#### *Sample Size*

As the scale of measurement for the VAS, SF-36, and the Oswestry Disability Scale are all on the ordinal scale, the Wilcoxon rank sum test will be used to compare the two groups. The sample size for the Wilcoxon rank sum test was calculated using the formulas derived by Noether. Forty-four people are needed in each group to insure a power of 90%, with an alpha of 0.05, and  $p'' = \text{probability}(Y > X) = 0.70$  where Y and X are random samples from two populations. Under the null hypothesis  $p'' = 0.50$ . To allow for lost to follow-up, fifty subjects will be recruited for each arm of the trial.

Sample size is predicted to be achieved within two years, estimating a yearly enrollment of 50 patients

[figure not shown]
## **Feasibility of Project**

- A) Time frame: 3 years
- B) Budget:**
  - a. Patients will be compensated \$50 each for completion of the study- \$5000. Patients will be paid \$20 at the first follow-up appointment and an additional \$30 at the final follow-up if their data set is complete.
  - b. SF-36 licensing fees: \$500 for 2 years.
  - c. Total- \$5,500
- C) **Available population:** Senior author is a major referral physician for coccygodynia. Expect to enroll 50 patients per year for 2 years. Previous treatments will be recorded to further characterize the study population and to determine its applicability to the general population of patients with this condition.
- D) **Equipment:** none

### **Visual Analog Scale**

## Figure 4

### **SF-36**

1. In general, would you say your health is:

- Excellent
- Very good
- Good
- Fair
- Poor

2. Compared to one year ago, how would you rate your health in general now?

- Much better now than a year ago
- Somewhat better now than a year ago
- About the same as one year ago
- Somewhat worse now than one year ago
- Much worse now than one year ago

3. The following items are about activities you might do during a typical day. Does your health now limit you in these activities? If so, how much?

a. Vigorous activities, such as running, lifting heavy objects, participating in strenuous sports.

- Yes, limited a lot.
- Yes, limited a little.
- No, not limited at all.

b. Moderate activities, such as moving a table, pushing a vacuum cleaner, bowling, or playing golf?

- Yes, limited a lot.
- Yes, limited a little.
- No, not limited at all.

c. Lifting or carrying groceries.

- Yes, limited a lot.
- Yes, limited a little.
- No, not limited at all.

d. Climbing several flights of stairs.

- Yes, limited a lot.
- Yes, limited a little.
- No, not limited at all.

e. Climbing one flight of stairs.

- Yes, limited a lot.
- Yes, limited a little.
- No, not limited at all.

f. Bending, kneeling or stooping.

- Yes, limited a lot.
- Yes, limited a little.
- No, not limited at all.

g. Walking more than one mile.

- Yes, limited a lot.
- Yes, limited a little.
- No, not limited at all.

h. Walking several blocks.

- Yes, limited a lot.
- Yes, limited a little.
- No, not limited at all.

i. Walking one block.

- Yes, limited a lot.
- Yes, limited a little.
- No, not limited at all.

j. Bathing or dressing yourself.

- Yes  No
- Yes  No
- Yes  No

4. During the past 4 weeks, have you had any of the following problems with your work or other regular daily activities as a result of your physical health?

a. Cut down the amount of time you spent on work or other activities?

- Yes  No

b. Accomplished less than you would like?

- Yes  No

c. Were limited in the kind of work or other activities

- Yes  No

d. Had difficulty performing the work or other activities (for example, it took extra time)

- Yes  No

5. During the past 4 weeks, have you had any of the following problems with your work or other regular daily activities as a result of any emotional problems (such as feeling depressed or anxious)?

a. Cut down the amount of time you spent on work or other activities?

- Yes  No

b. Accomplished less than you would like

- Yes  No

c. Didn't do work or other activities as carefully as usual

- Yes  No

6. During the past 4 weeks, to what extent has your physical health or emotional problems interfered with your normal social activities with family, friends, neighbors, or groups?

- Not at all
- Slightly
- Moderately
- Quite a bit
- Extremely

7. How much bodily pain have you had during the past 4 weeks?

- Not at all
- Slightly
- Moderately
- Quite a bit
- Extremely

8. During the past 4 weeks, how much did pain interfere with your normal work (including both work outside the home and housework)?

- Not at all
- Slightly
- Moderately
- Quite a bit
- Extremely

9. These questions are about how you feel and how things have been with you during the past 4 weeks. For each question, please give the one answer that comes closest to the way you have been feeling. How much of the time during the past 4 weeks.

a. did you feel full of pep?

- All of the time
- Most of the time
- A good bit of the time
- Some of the time
- A little of the time
- None of the time

b. have you been a very nervous person?

- All of the time
- Most of the time
- A good bit of the time
- Some of the time
- A little of the time
- None of the time

c. have you felt so down in the dumps nothing could cheer you up?

- All of the time
- Most of the time
- A good bit of the time
- Some of the time
- A little of the time
- None of the time

d. have you felt calm and peaceful?

- All of the time
- Most of the time
- A good bit of the time
- Some of the time
- A little of the time
- None of the time

e. did you have a lot of energy?

- All of the time
- Most of the time
- A good bit of the time
- Some of the time
- A little of the time
- None of the time

f. have you felt downhearted and blue?

- All of the time
- Most of the time
- A good bit of the time
- Some of the time
- A little of the time
- None of the time

g. did you feel worn out?

- All of the time
- Most of the time
- A good bit of the time
- Some of the time
- A little of the time
- None of the time

h. have you been a happy person?

- All of the time
- Most of the time
- A good bit of the time
- Some of the time
- A little of the time
- None of the time

i. did you feel tired?

- All of the time
- Most of the time
- A good bit of the time
- Some of the time
- A little of the time
- None of the time

10. During the past 4 weeks, how much of the time has your physical health or emotional problems interfered with your social activities (like visiting friends, relatives, etc.)?

- All of the time
- Most of the time
- Some of the time
- A little of the time
- None of the time

11. How TRUE or FALSE is each of the following statements for you?

a. I seem to get sick a little easier than other people

- Definitely true
- Mostly true
- Don't know
- Mostly false
- Definitely false

b. I am as healthy as anybody I know

- Definitely true
- Mostly true
- Don't know
- Mostly false
- Definitely false

c. I expect my health to get worse

- Definitely true
- Mostly true
- Don't know
- Mostly false

- Definitely false
- d. My health is excellent
  - Definitely true
  - Mostly true
  - Don't know
  - Mostly false
  - Definitely false

## Figure 5

### **The Oswestry Disability Index (ODI) Version 2.0 or Oswestry Low Back Pain Disability Questionnaire**

#### **Section 1: Pain Intensity**

- I can tolerate the pain I have without having to use pain killers. [0 points]
- The pain is bad but I manage without taking pain killers. [1 point]
- Pain killers give complete relief from pain . [2 points]
- Pain killers give moderate relief from pain. [3 points ]
- Pain killers give very little relief from pain. [4 points]
- Pain killers have no effect on the pain and I do not use them. [5 points]

#### **Section 2: Personal Care**

- I can look after myself normally without causing extra pain. [0 points]
- I can look after myself normally but it causes extra pain. [1 point]
- It is painful to look after myself and I am slow and careful. [2 points]
- I need some help but manage most of my personal care. [3 points]
- I need help every day in most aspects of self care. [4 points]
- I do not get dressed wash with difficulty and stay in bed. [5 points]

#### **Section 3: Lifting**

- I can lift heavy weights without extra pain. [0 points]
- I can lift heavy weights but it gives extra pain. [1 point]
- Pain prevents me from lifting heavy weights off the floor but I can manage if they are conveniently positioned for example on a table. [2 points]
- Pain prevents me from lifting heavy weights but I can manage light to medium weights if they are conveniently positioned. [3 points]
- I can lift only very light weights. [4 points]
- I cannot lift or carry anything at all. [5 points]

#### **Section 4: Walking**

- Pain does not prevent me walking any distance. [0 points]
- Pain prevents me walking more than 1 mile. [1 point]
- Pain prevents me walking more than 0.5 miles. [2 points]
- Pain prevents me walking more than 0.25 miles. [3 points]

- I can only walk using a stick or crutches. [4 points]
- I am in bed most of the time and have to crawl to the toilet. [5 points]

#### **Section 5: Sitting**

- I can sit in any chair as long as I like. [0 points]
- I can only sit in my favorite chair as long as I like. [1 point]
- Pain prevents me sitting more than 1 hour. [2 points]
- Pain prevents me from sitting more than 0.5 hours. [3 points]
- Pain prevents me from sitting more than 10 minutes. [4 points]
- Pain prevents me from sitting at all. [5 points]

#### **Section 6: Standing**

- I can stand as long as I want without extra pain. [0 points]
- I can stand as long as I want but it gives me extra pain. [1 point]
- Pain prevents me from standing for more than 1 hour. [2 points]
- Pain prevents me from standing for more than 30 minutes. [3 points]
- Pain prevents me from standing for more than 10 minutes. [4 points]
- Pain prevents me from standing at all. [5 points]

#### **Section 7: Sleeping**

- Pain does not prevent me from sleeping well. [0 points]
- I can sleep well only by using tablets. [1 point]
- Even when I take tablets I have less than 6 hours sleep. [2 points]
- Even when I take tablets I have less than 4 hours sleep. [3 points]
- Even when I take tablets I have less than 2 hours of sleep. [4 points]
- Pain prevents me from sleeping at all. [5 points]

#### **Section 8: Sex Life**

- My sex life is normal and causes no extra pain. [0 points]
- My sex life is normal but causes some extra pain. [1 point]
- My sex life is nearly normal but is very painful. [2 points]
- My sex life is severely restricted by pain. [3 points]
- My sex life is nearly absent because of pain. [4 points]
- Pain prevents any sex life at all. [5 points]

#### **Section 9: Social Life**

- My social life is normal and gives me no extra pain. [0 points]
- My social life is normal but increases the degree of pain. [1 point]
- Pain has no significant effect on my social life apart from limiting energetic interests such as dancing. [2 points]
- Pain has restricted my social life and I do not go out as often. [3 points]
- Pain has restricted my social life to my home. [4 points]
- I have no social life because of pain. [5 points]

#### **Section 10: Traveling**

- I can travel anywhere without extra pain. [0 points]

- I can travel anywhere but it gives me extra pain. [1 point]
- Pain is bad but I manage journeys over 2 hours. [2 points]
- Pain restricts me to journeys of less than 1 hour. [3 points]
- Pain restricts me to short necessary journeys under 30 minutes. [4 points]
- Pain prevents me from traveling except to the doctor or hospital. [5 points]

**Interpretation:**

**ODI Scoring:**

- **0% to 20% (minimal disability):** Patients can cope with most activities of daily living. No treatment may be indicated except for suggestions on lifting, posture, physical fitness and diet. Patients with sedentary occupations (ex. secretaries) may experience more problems than others.
- **21%-40% (moderate disability):** Patients may experience more pain and problems with sitting, lifting and standing. Travel and social life are more difficult. Patients may be off work. Personal care, sleeping and sexual activity may not be grossly affected. Conservative treatment may be sufficient.
- **41%-60% (severe disability):** Pain is a primary problem for these patients, but they may also be experiencing significant problems in travel, personal care, social life, sexual activity and sleep. A detailed evaluation is appropriate.
- **61%-80% (crippled):** Back pain has an impact on all aspects of daily living and work. Active treatment is required.
- **81%-100%:** These patients may be bed bound or exaggerating their symptoms. Careful evaluation is recommended.

**Figure 6: Questionnaire**

[figure not shown]
### Coccygodynia Questionnaire

To be completed at enrollment, 2 weeks, 6 weeks, 3 months, 6 months and 1 year after treatment

Date of Treatment \_\_\_\_\_  
Today's Date \_\_\_\_\_

Pt name \_\_\_\_\_  
MRN \_\_\_\_\_

1. Please draw a vertical mark (like this: |) on the line below, which best describes the amount of pain you feel where your tailbone is or was.

2. What medicines are you currently taking to control or treat pain at the site where your tailbone is or was? Please include the dose and how often you take the medicine.

3. Are you taking the medicines you have listed above in question 2 every day? For each medicine listed in your response to question 2, please write YES or NO.

4. Please check the most appropriate box for you regarding sitting.

- I can sit in any chair as long as I like.
- I can only sit in my favorite chair as long as I like.
- Pain prevents me from sitting more than 1 hour.
- Pain prevents me from sitting more than 0.5 hours.
- Pain prevents me from sitting more than 10 minutes.
- Pain prevents me from sitting at all.

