rest, and cushion support. Rarely, physical therapy with diathermy and ultrasound may be prescribed, although there is no evidence to support its role. After initial conservative management, corticosteroid injections may be performed. Wray et al reported a cure rate of 59% with local steroid injection alone, and an 85% cure rate when injection was combined with manipulation under anesthesia. There was a 21% relapse rate in this group of patients (11). Maigne and Chatellier attempted conservative treatment with levator ani muscle massage, joint mobilization and stretching exercises and found only a 25% success rate (7).

*Surgical Treatment:*

When conservative treatment for coccygodynia fails, removal of the coccyx (coccygectomy) may be considered. Both significant, disabling pain and radiographic abnormalities should be present before surgical consideration. Surgery consists of either complete removal of the coccyx or excision of the mobile segment. The most common complication is wound infection and dehiscence due to perineal contamination (8, 10). Maigne et al prospectively followed 37 patients treated with coccygectomy and found 34 of 37 had good to excellent results at minimum of 2 years. Doursounian et al reported on 61 patients treated with coccygectomy, which is the largest retrospective case series published (3). They found good to excellent results in 53 of 61 patients. Nine patients in this study developed an infection requiring re-operation. Wood and Mehbod compared 20 patients treated with coccygectomy to 25 patients treated with corticosteroid injections. They found 90% of patients treated surgically felt improvement whereas only 20% of patients treated with injections felt improvement. This study however was not randomized and decision to treat operatively was made by the senior author leading to significant selection bias.

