**D) Definition of Variables**

- a. **Outcome Variables:** Visual Analog Scale for pain intensity, Short-Form 36, Oswestry Disability Scale, Tolerable sitting time, wound complications, intra-operative complications
- b. **Independent Variables:** Age, gender, co-morbidities, type of coccygeal morphology
- c. **Potential Confounding Variables:** Disability status, pain medications prescribed by other physicians, co-existing musculoskeletal disease.

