#### **Statistical Procedures for Analysis and Sample Size Determination**

Standard statistical tests will be used. Descriptive statistics including means and standard deviations, or counts and percentages will be reported. As the scale of measurement for the VAS, SF-36, and the Oswestry Disability Scale are all on the ordinal scale, the Wilcoxon rank sum test will be used to compare the two groups (pre- and post-operative). Complication rates will be calculated.

A p-value of less than 0.05 will be considered statistically significant. The SAS software will be used for all analyses.

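### Injection, manipulation or further coccyx surgery after coccygectomy is never asked about, so scores obtained after such procedures are credited to the operation

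*Combined protocol and SAP*

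**What the plan says.** **What is recorded after surgery.** Figure 6 has four items: a pain line, current medicines, whether each is taken daily, and a sitting category. Its only treatment question is "What medicines are you currently taking to control or treat pain at the site where your tailbone is or was".

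**Variables.** Section D, Definition of Variables, lists the pain and function scales as outcomes, plus complications of the wound and complications during the operation. The independent variables are "Age, gender, co-morbidities, type of coccygeal morphology". The confounders include analgesics prescribed elsewhere, but no procedures.

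**Treatment history.** Feasibility of Project, item C, states: "Previous treatments will be recorded to further characterize the study population". This concerns treatment before enrollment.

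**Analysis.** Statistical Procedures plans a rank sum test of pre-operative against post-operative scores, plus complication rates. It has no rule for a score obtained after another procedure. The second purpose is to find predictors of good outcomes, but the plan does not define a good outcome.

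**Background.** For local steroid injection alone the plan cites 59% cure; it also cites "an 85% cure rate when injection was combined with manipulation under anesthesia". The same series had 21% relapse. In a separate comparative series, 20% improved with injection.

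**The concern.** The study has no true control group, so the change from before to after surgery is the whole evidence for the operation. Follow-up runs to 2 years. The operation removes only the mobile segment, and eligibility requires failure of NSAIDs, cushion and rest but not of injection. Injection, manipulation and further excision therefore all remain possible afterwards, and they would go mainly to patients whose pain persists.

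Take a patient with persistent pain who has an injection at month 5 and is comfortable at 1 year. At 1 year the injection is no longer a medicine currently taken, so the form has no place for it. The 3-month pain score would show the persistent pain. SF-36 and Oswestry are collected after surgery only at 1 year, so on those scales no score exists from before the injection. The improved scores are read as the effect of coccygectomy. If the date is not collected, the analysis cannot separate the two treatments later.

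The predictor aim is affected too, because a patient who did poorly after surgery but well after a later procedure looks like a good surgical outcome.

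**Working it through.** **1. The plan's own figure.** The Sample Size section states: "Forty-four people are needed in each group to insure a power of 90%, with an alpha of 0.05", with P(Y > X) = 0.70 against 0.50. Noether's formula with equal groups, two-sided, gives N = (1.960 + 1.282)² / [12 × 0.25 × (0.70 − 0.50)²] = 87.56, or 43.78 per group, which rounds up to 44. The figure is reproduced, and this point does not change it.

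**2. Number of completers.** Enrollment of 50 a year for 2 years gives 100 patients. The plan raises 44 to 50 for loss to follow-up, so it expects 44/50 = 88% to complete: 88 patients.

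**3. Share having a later procedure, r.** The documents give no rate.
- Lower end: 5%, an assumption. 88 × 0.05 = 4.4 patients.
- Upper end: every failure implied by the largest cited surgical series, where 53 of 61 did well. 8/61 = 13.1%, and 88 × 8/61 = 11.5 patients.
- The other cited surgical figures imply fewer failures: 3/37 = 8.1% (7.1 of 88), and 10% not improved (8.8 of 88).

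**4. Share responding, c.** The cited figures are 20%, 59% and 85%. None is a rate after failed coccygectomy, so they only mark out a range.

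**5. Patients affected = 88 × r × c.**

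| r | c = 20% | c = 59% | c = 85% |
|---|---|---|---|
| 5% | 0.9 (1.0%) | 2.6 (2.95%) | 3.7 (4.25%) |
| 13.1% | 2.3 (2.6%) | 6.8 (7.7%) | 9.8 (11.1%) |

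The range is about 1 to 10 patients, or 1% to 11% of completers. With 44 completers the counts halve and the percentages stay the same.

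**6. Effect on the planned test.** Suppose a failed patient scores like the baseline distribution and so contributes 0.5 to P(Y > X). A response to a later procedure raises that contribution to at most 1, so P(Y > X) rises by at most 0.5 × r × c.
- Low end: 0.5 × 0.05 × 0.20 = 0.005, so an observed 0.70 would be 0.695 without the later procedures.
- High end: 0.5 × 0.131 × 0.85 = 0.056, so 0.70 would be 0.644.

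On Noether's scale at 44 per group, z = √(12 × 0.25 × 88) × (P − 0.50). For 0.70 this is 16.25 × 0.20 = 3.25; for 0.644 it is 16.25 × 0.144 = 2.34. Both exceed 1.96. This treats pre and post scores as independent samples, as the plan's formula does.

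**The case against.** **Data collection is wider than Figure 6.** The form also has no items for complications, co-morbidities or previous treatments, all of which the plan intends to record. A re-operation for infection could surface as a wound complication, and a recent injection might be written under the medicines item. This stands as far as it goes. But the plan does state that those other data will be recorded and makes no such statement for later procedures. For patients followed by phone or mail, the form may be the only source.

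**The cited rates do not measure rescue.** This stands. A reader might take from the Background that manipulation alone cures 85%. That figure belongs to injection combined with manipulation, and no rate is given for manipulation alone. The 21% relapse and the 20% improvement figure must be read beside the favorable ones.

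**Nobody is literally counted as a success.** A reader might infer that rescued patients are classified as coccygectomy successes. The plan defines no responder endpoint. What happens is that improved scores enter a rank comparison.

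**Pooling patients with and without prior injection.** A reader might infer that this biases the pre/post comparison. It does not. Prior injection or manipulation is only a candidate predictor missing from the list, and the analysis section specifies no predictor analysis in any case.

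**A harsh scoring rule would do its own damage.** Giving the worst rank of change after any further operation does not fit a test that compares scores rather than changes. It would also score infection re-operations as pain failures: at the cited 9/61, 88 × 9/61 = 13 patients. This stands, and the remedy below avoids it.

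**Conclusion.** The gap is real and of moderate size. The plan neither records procedures for coccyx pain after surgery nor says how scores obtained after them are handled, and in a single-group study those scores are attributed to coccygectomy. Under the assumptions shown (5% to 13% having a procedure, 20% to 85% responding), about 1 to 10 of 88 completers are affected. Both inputs are assumptions: the lower procedure rate is chosen for illustration, the upper one requires every failure to have a procedure, and the response rates come from other settings.

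A reader might infer that the overall conclusion of benefit would be overturned. The calculation does not support that: at the planning effect size, even the high end leaves the comparison above the significance threshold. The likely harm is an inflated estimate of benefit and blurred predictors.

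**What to change.** 1. Add one dated item to Figure 6, also asked by phone or mail, for example: *Since your last form, have you had an injection, manipulation or another operation for your tailbone? Give the reason and date.* The form's heading stops at 1 year while the design summary follows patients to 2 years, so state that the item is asked at 2 years as well.
2. Report how many patients had each type of procedure, with reason and timing.
3. Keep the as-observed pre/post comparison as the main result.
4. Prespecify a sensitivity analysis in which scores after a procedure done for persistent pain are replaced by the patient's baseline score, meaning no improvement. This works on the planned score scale.
5. Keep re-operations for wound infection under wound complications and do not treat them as pain failures.
6. Optionally, add prior injection or manipulation, already to be recorded, to the independent variables for the predictor aim.

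The cost is one form line and a few sentences of analysis text. No care is restricted and no visit is added. The sensitivity result may be slightly less favorable than the main one.
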